In this hybrid effectiveness-implementation study, both data on implementation process, and adolescent outcomes will be captured. A mixed-methods process evaluation will describe the programme implementation, context, and mechanisms of action. The study cohort will be followed up for approximately 12 months with adolescent process and outcome data collected at screening, 4-month and 12-month follow-up visits (**Figure 2**). An economic evaluation will estimate unit costs per adolescent screened, condition identified and case treated, and estimate the cost-effectiveness of the intervention in improving adolescent well-being. Where data are available, we will estimate the impact

of the intervention on DALYs averted. We will gather information to develop methodologies for a potential larger future study to measure the longer-term health, well-being and educational impact of the programme. We will assess the scale up and financial sustainability of the programme.

The prospective intervention study design is more appropriate than a randomised controlled trial (RCT) for answering the research question because i) it is impossible to measure the adolescent outcomes in the absence of the screening which is an integral part of the Y-Check intervention; ii) the intervention components are known to be effective for identifying conditions for which known effective interventions exist (e.g. Provision of spectacles for adolescents with myopia; provision of psychological interventions by trained lay mental health providers through the "Friendship Bench" approach for adolescents with symptoms of significant common mental health disorders), so a control arm in which adolescents were screened, found to have these conditions but not offered care would be unethical; and iii) the great majority of conditions being screened for are chronic, so the prevalence of previously undiagnosed and untreated conditions or risky behaviours provides its own counterfactual reflecting a lack of prior appropriate diagnosis and effective treatment.

COVID-19, which the WHO declared a pandemic on 11 March 2020, has had significant effects on research activities worldwide. Over the past 18 months, adaptations to procedures have allowed research activities to continue in a safe environment for research staff and participants.

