All Y-Check procedures will be conducted in well-aerated tents or outdoors to minimise risk during screening tests, physical examinations, and blood tests. Standard infection prevention and control (IPC) protocols will be implemented with all staff and participants wearing appropriate surgical or cloth masks. If a participant does not have a suitable mask, the research team will provide a new surgical mask. In addition, all staff and participants will wash their hands before interacting. Finally, all working surfaces and instruments will be sanitised between each participant. If standard COVID-19 IPC protocols cannot be implemented in school settings, the Y-Check service will be temporarily delivered in the community until a suitable solution is found.

If there is a suspected COVID case, we will follow the national guidelines that are current at the time. Y-Check will use opportunity to advocate for all adolescents who are eligible for Covid-19 vaccination locally who attend the Y-Check-Up to avail themselves of this opportunity and will provide information on where they might go to get vaccinated.

Social distancing, handwashing, and sanitisation of surfaces will also be implemented during all interviews and focus group discussions.

**Phase 3 (Knowledge dissemination and translation)** will involve statistical analysis, mathematical modelling, refinement of programme guidelines, report writing, dissemination of study findings to young people and other stakeholders, and the development of research proposals.

Figure 2: Timeline of Study

	2021			2022			2023				2024					
	Q1	Q2	Q3	Q4	Q1	Q2	Q3	Q4	Q1	Q2	Q3	Q4	Q1	Q2	Q3	Q4
Inception	*	*														
Intervention development and pilot testing			*	*	*	*										
Implementation of Y-Check							*	*	*	*						
Research cohort recruitment							*	*	*	*						
Follow-up at 4 & 12 months								*	*	*	*	*	*	*		
Process and economic evaluation							*	*	*	*	*	*	*	*		
Analysis & reporting													*	*	*	*

[figure not shown]

Figure 3: Y-CHECK logic model

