#### 3.7.4 Intervention team

There will be two intervention teams, each comprising of a two nurses, a counsellor, and three or four research assistants. The team will consist of a mix of male and female providers. The Y-Check team(s) will spend approximately 2-3 weeks in each school for the check-up visit. The Y-Check 2 teams(s) will spend 3-5 weeks delivering the check-up visit in each community hub.

Although the intervention teams are affiliated with this research project (and this will be made clear to all those who interact with them), their primary role will be to deliver what is recognized by the WHO as 'best practice' public health interventions. Hence for this project we regard the intervention teams as separate from the 'research teams' and believe that the norms and standards governing their activities should largely be those accepted for the implementation of public health interventions rather than those applied to conventional clinical research projects. Regarding the services being delivered by the intervention team as research activities would make this public health research project logistically impossible to implement.

The intervention team will be selected on the basis of prior experience in working in communities and with adolescents. In addition, the intervention team will undergo a training programme on provision of youth friendly services as well as on each of the intervention components. Training will particularly focus on the following aspects:

• Adolescent physiology and development

- Knowledge and skill on delivery of each intervention component according to age and maturity
  of client
- Skills on counselling and communication with adolescents
- Skills to bring myths to surface, and to discuss and dispel them
- Interpersonal skills
- Adolescent rights
- Attitudinal training (respect, confidentiality, non-judgement, relatability)
- Referral pathways
- Gendered vulnerabilities and gender responsive health services

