## **Prospective Intervention study**

We will follow the STROBE guidelines for the reporting of cohort studies. We will create a flowchart showing the number of communities and schools and the number of participants per community and school at each contact point in the cohort study. We will use descriptive analysis to compare the community-level and school-level characteristics of the four study communities and schools.

The primary outcome is a single proportion which will be presented with a 95% confidence interval for each of the 4 target populations: 10-13y male, 10-13y female, 16-19y male, 16-19y female. Secondary outcomes which are measured at a single time point will be presented in a similar way. For outcomes which are measured at two or more time-points, a before-after analysis will be conducted comparing differences in measures between the two time-points. The unit of analysis will be the individual. For clinical outcomes which are measured at two or more time-points, the initial check-up visit (baseline) will give the prevalence of undiagnosed and untreated chronic conditions which will represent the counterfactual. The proportion of undiagnosed and untreated chronic conditions at the 4-month follow-up visit will be formally compared to this counterfactual to estimate the effectiveness of the intervention in improving these clinical outcomes. We will assess health service and client determinants of correct management of conditions at 4 months using multivariable regression.

**Digital platform data** De-identified data on information viewed, games played, rewards provided/used along with programmatic data on behaviours and clinical conditions etc. will be analysed using machine learning approaches to understand the sub-groups/segments of adolescents who participate in Y-Check. This analysis will help us to define, develop, and pilot test targeted messaging for different sub-groups of young people who attend Y-Check follow-up visits. We will also analyse this data to develop algorithms which could potentially be used in the future phases of the Y-Check programme to further personalise the Y-Check user experience to maximise relevance, uptake and retention.

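### Before-after changes in non-chronic outcomes are read as programme impact with no allowance for calendar time; they should be called changes, with a calendar-adjusted sensitivity analysis beside them where the timeline allows

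*Protocol*

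**What the plan says.** Section 6.3 (Prospective Intervention study) applies a before-after comparison to every outcome measured more than once: "For outcomes which are measured at two or more time-points, a before-after analysis will be conducted comparing differences in measures between the two time-points". It adds "The unit of analysis will be the individual". For clinical outcomes it names the baseline prevalence of undiagnosed, untreated chronic conditions as the counterfactual and continues: "The proportion of undiagnosed and untreated chronic conditions at the 4-month follow-up visit will be formally compared to this counterfactual", in order "to estimate the effectiveness of the intervention in improving these clinical outcomes".

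The causal reading is not confined to that sentence. Objective 2(iii) in section 2.2 is to estimate short-term programme impact on knowledge, behaviours and well-being, among other outcomes. Section 4.3.4 makes cost per improvement in well-being a primary economic objective.

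The defence is in section 2.3. One reason given for preferring this design to a randomised trial is that "it is impossible to measure the adolescent outcomes in the absence of the screening which is an integral part of the Y-Check intervention". Another is that most conditions are chronic, "so the prevalence of previously undiagnosed and untreated conditions or risky behaviours provides its own counterfactual".

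On timing, section 3.7.4 has two teams that "spend approximately 2-3 weeks in each school for the check-up visit" and 3 to 5 weeks in each community hub. Figure 2 shows recruitment from Q3 2022 to Q2 2023, and the row "Follow-up at 4 & 12 months" starts in Q4 2022, while recruitment is still running.

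**The concern.** A person's own baseline is a fair counterfactual only if the outcome would have stayed put without the programme. That is plausible for visual or physical impairment. It is not for symptom severity, well-being, self-esteem, diet, activity, anaemia or STI, all of which can move over 4 months for reasons unrelated to Y-Check.

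The protocol itself names outside influences: national PrEP roll-out (3.7.2), a national HPV programme aimed at Grade 5, the likely Y-Check 1 grade (3.7.2 and 3.7), and COVID-19 disruption (2.3). PrEP use and HPV immunisation are both listed as outcomes in Appendix 1. The stated analysis would credit any such change to the programme, and the result would feed the impact objective, the cost-effectiveness ratio and the planning estimates for a larger study. The primary outcome is a single proportion and is not affected.

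**Working it through.** **Inputs.** From the protocol: 1,000 per age group; 4–6 primary schools, 2–8 secondary schools, 2–4 community venues (2.3); two teams and their weeks per site (3.7.4); Figure 2. Section 6.2 gives no power, effect size or precision for any before-after comparison, so there is no stated figure to reproduce. Assumed: baseline prevalence, within-person correlation ρ of 0.3–0.5, size of the general change d, zero programme effect.

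**1. How often a general change looks like an effect.** With p₁ = p₀ − d,

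SE = √{[p₀(1−p₀) + p₁(1−p₁) − 2ρ√(p₀(1−p₀)p₁(1−p₁))] / N}

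P(significant) = Φ(d/SE − 1.96) + Φ(−d/SE − 1.96).

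For p₀ = 0.25, d = 0.03, N = 1,000, the variance terms are 0.1875 and 0.1716 and the root of their product is 0.1794. With ρ = 0.3, SE = √(0.2515/1000) = 1.59 points; with ρ = 0.5, SE = √(0.1797/1000) = 1.34 points. The site-level column puts the same d/SE into a paired t-test on 6 site differences (5 df).

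| General change over 4 months | Individual-level, 25% baseline | Individual-level, 20% baseline | Site-level, 6 sites, 25% baseline |
|---|---|---|---|
| 1 point | 10–11% | 10–13% | 8–9% |
| 3 points | 47–61% | 54–69% | 34–44% |
| 5 points | 89–97% | 94–99% | 73–85% |

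The nominal rate is 5%. A fair summary is about 10%, roughly half, and about 85%. At 10% baseline, a 3-point change gives 82–92% (individual-level).

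**2. Whether concurrent baselines exist.** If entry is even over T months, the share of 4-month follow-ups falling inside the recruitment window is max(0, 1 − 4/T): 67% for the 12 months of Figure 2, 50% for 8, 33% for 6, 0% for 4. For the 12-month visit it is zero for any T up to 12. Site time is 6–14 schools × 2–3 weeks + 2–4 hubs × 3–5 weeks = 18–62 team-weeks, or 9–31 weeks with two teams, against about 17 weeks to the 4-month visit. Overlap is therefore likely under Figure 2 but not guaranteed.

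**3. What a calendar-adjusted model can identify.** A site entering at time tₛ is seen at tₛ and tₛ + 4. For every record, exposure = (t − tₛ)/4. Period terms span t, and fixed site effects span tₛ, so with both in the model the exposure effect is an exact linear combination of the other terms and cannot be estimated. A random site effect makes it estimable, but only through differences between sites.

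**4. Precision.** Assumed: prevalence 20%, N = 1,000, 85% retention, ρ = 0.4, ICC 0.01, cluster autocorrelation 0.8, 2-month periods. Half-widths of the 95% interval, in points:

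| Sites, recruitment | Before-after | With period terms | Ratio |
|---|---|---|---|
| 6 over 12 months | 3.5 | 5.9 | 1.7 |
| 6 over 6 months | 3.5 | 10.1 | 2.9 |
| 4 over 12 months | 3.8 | 13.3 | 3.5 |
| 4 over 4 months | 3.8 | not estimable | – |

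**5. Site order.** Simulation with a correlation of 0.5 between a site's underlying level and its place in the order biases the adjusted estimate by about 3 points.

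**The case against.** Several points on the other side stand.

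- No document figure supports a 3- or 5-point change, and at 1 point the false-signal rate is only about twice nominal.
- The explicit counterfactual wording in 6.3 concerns chronic conditions, where the argument of 2.3 has force.
- A 12-month visit falls in the same season as baseline, which partly answers the seasonal worry for that comparison.
- Adjustment terms often belong in the statistical analysis plan. Here, though, the protocol itself fixes the comparison and the counterfactual.

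A reader might infer that staggered entry supplies a free, unbiased control group that the plan throws away. The documents do not support that. Site order is neither fixed nor randomised. Community engagement, provider training and mobile outreach (3.3, 3.5, 3.7) may reach later sites before their check-ups. The comparison must stay within age group and setting. For STI, tested only in community hubs (3.7.2), that leaves 2–4 sites.

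A reader might also pool all sites. That raises the false-signal rate at 3 points to about 76%, but mixes populations with different ages, settings and test content, and overstates the available precision as well.

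It would be tempting to accept a before-after change as a programme effect whenever the adjusted estimate has the same sign. With no true effect the adjusted estimate is centred on zero, so such a rule still passes about 44–52% of pooled null studies at 3–5 points of drift.

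Nor does section 2.3 claim that no comparison is possible. It argues only against a randomised trial.

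**Conclusion.** The point holds in a limited form. For non-chronic outcomes the own-baseline comparison cannot separate programme impact from general change, and the chronic-condition argument does not repair this. Within one age group of 1,000, a 3-point change with no programme effect would appear significant in roughly half of studies, given the assumed prevalence and within-person correlation. The size of any real drift is unknown.

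The overlap in Figure 2 permits a useful sensitivity analysis of the 4-month comparison, not a substitute for a control group. It may be uninformative or impossible with few sites or rapid recruitment, and it offers nothing at 12 months. The case is weaker for truly chronic conditions.

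**What to change.** In section 6.3:

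1. Describe before-after differences in non-chronic outcomes, and all 12-month differences, as changes and not as effectiveness or impact. Carry the same wording into objective 2(iii) and the well-being cost ratio.
2. Where recruitment and 4-month follow-up overlap, add a supplementary analysis of all baseline and 4-month records of the whole cohort, separately by age group and setting. Include exposure (before or after own check-up), calendar-period terms and a random site effect, and allow for repeated measures on a participant. Using the whole cohort and not only baseline screen-positives avoids regression to the mean.
3. Report that estimate and interval beside the before-after change, with no rule based on agreement in sign.
4. State its limits: it rests on between-site differences, later sites may be partly exposed, and it may not be estimable.
5. Where schools have no preference, set the order of visits by lot.

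The cost is wording, one extra model and a small scheduling step; no new data are collected. The price is an interval about 1.7 to 3.5 times wider with 4–6 sites per age group at ICC 0.01. At ICC 0.03 over 12 months the ratio is 1.9 with 6 sites (4.5 to 8.4 points) and 3.9 with 4 sites (5.2 to 20.5 points).

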# 2.3 Study design

During **Phase 1** (**Intervention development and piloting**) we will use a variety of processes and methodologies including community engagement, participatory co-design, qualitative interviews and discussions, health register and school register review, and validation and pre-testing of screening tools, procedures and referral protocols. Locally accessible services will be identified and pre-tested to confirm that they are acceptable and accessible from multiple perspectives, including adolescents themselves. An extended period of piloting will involve the piloting of the screening tools and procedures for each of the target conditions and behaviours with revisions and repeat piloting where required. Up to 200 participants will be involved in the piloting of screening tools and procedures. There will be an opportunity for young people and stakeholders to suggest additional relevant outcomes that may reflect some of their priority concerns/intentions that should be captured (Client-centered outcomes).

During Phase 2 (Implementation and evidence generation) we will conduct a prospective intervention study (cohort study) in Chitungwiza, Zimbabwe to assess the feasibility of the intervention and to evaluate the short-term impact of the intervention. The intervention will be implemented for 10-14 year olds in 4-6 primary schools (N=1000, Y-Check 1), 15-19 year olds at 2-8 secondary schools, and 16-19 year olds at 2-4 community venues (N=1000, Y-Check 2). The intervention does not intend to target all adolescents but instead to focus on two time points during the adolescent period: early adolescence (10-14) years at or just before the onset of puberty, and middle/late adolescence (15-19 years) when many adolescents become or are soon to become sexually active. The exact target school grades and age-ranges will be agreed in consultation with MoPSE, MoHCC and other stakeholders during Phase 1 of the study.

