# 3.2 Setting

Chitungwiza is the third largest city in Zimbabwe, located approximately 25km south of the capital city, Harare, and has a population of about 456 000. The houses are mostly high-density, single story, detached units with small yards that are generally used for growing vegetables. Most of the people work in Harare, as there is little industry in Chitungwiza. There is one tertiary hospital, 4 public primary healthcare facilities, 20 private medical facilities, and 34 government primary schools (all mixed sex).

Four communities and four schools were chosen by Chitungwiza stakeholders to take part in Y-Check formative work in 2019/20 (High schools: Seke High 6, Zengeza High 1; Primary schools: Dungwiza Primary, Chinembiri Primary). Communities and schools were selected to represent the diversity of wards in the town and taking into account the economic disparities. The selection of the schools and communities for this study will be conducted in collaboration with stakeholders including MoPSE, MoHCC, and the study Youth Advisory Group (YAG) taking into consideration previous participation in the formative work and the location of other ongoing projects. We will aim to work in four distinct communities which are representative of the urban, peri-urban and rural populations of Chitungwiza. Potentially eligible schools must meet the following criteria:

- Student population of at least 200 learners in Grade 5, 6, or 7 (Y-Check 1 target intervention year) or at least 75 learners in Form 3, 4 or 5 (Y-Check 2 target intervention year).
- Located in or close to one of the selected study communities

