• School recruitment (Y-Check 1 (10-14y) & Y-Check 2 (15-19y)): All students in the Y-Check target classes/forms will be eligible to participate if their parent/guardian has signed a consent form and the student has provided written assent.

• Community recruitment (Y-Check 2 (16-19y)): Participants receiving Y-Check 2 services in the community will provide their own verbal consent. Parent/guardian consent will not be required for adolescents receiving services in the community, but participants will be encouraged to share information and results with their parents/guardians or another trusted adult.

Parents/guardians/students can choose to participate in the full screening visit or part of the screening visit e.g. the pre-consultation questionnaire and nurse review only.

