# 6.2 Sample size calculations

The package will be delivered to 2000 adolescents (500 per gender in each age group), however, the primary outcome is only measured among those who screen positive for at least one condition. Within one age group and gender, if 150 (30%) of 500 participants screen positive for at least one condition, and 75% of those who screen positive are correctly managed (n=112; primary outcome), the 95%CI for correct management will be  $\pm 1.7\%$ .

The sample size also allows us to describe prevalence of individual conditions, and proportion with corrective action taken (secondary outcomes). For example, if 50 of 1000 participants in one age group

(5%) screen positive for a given condition, and 75% of these have complete referral, the 95%CI will be 62%-87%, or a 95%CI of 35%-65% if 50% complete referral.

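### Planned precision in section 6.2 makes no allowance for clustering by school or hub, and section 6.3 sets the individual as the unit of analysis without allowing for site

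*Protocol*

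**What the plan says.** Section 2.3 of the protocol places the intervention in a small number of sites: "10-14 year olds in 4-6 primary schools (N=1000, Y-Check 1), 15-19 year olds at 2-8 secondary schools, and 16-19 year olds at 2-4 community venues". Y-Check 1 therefore has 4-6 sites and Y-Check 2 has 4-12 (2+2 up to 8+4). Section 3.2 adds that "The selection of the schools and communities for this study will be conducted in collaboration with stakeholders", so sites are chosen and not sampled. Within a school, section 3.7 says "All students in the Y-Check target classes/forms will be eligible to participate", subject to consent and assent.

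Section 6.2 takes 150 screen-positives among 500 participants in one age and sex group, with 75% correctly managed, and gives a 95% confidence interval of ±1.7%. For a single condition with 50 screen-positives in an age group it says "75% of these have complete referral, the 95%CI will be 62%-87" percent, and 35%-65% if half complete referral. It mentions no ICC and no design effect.

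Section 6.3 plans a proportion with a 95% interval in each of four age-sex groups, before-after comparisons, and a regression: "We will assess health service and client determinants of correct management of conditions at 4 months using multivariable regression". It fixes the unit in one sentence: "The unit of analysis will be the individual". School and community appear there only in a flowchart and a descriptive comparison. No interval method or variance estimator is named.

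**The concern.** The protocol itself gives reasons to expect outcomes within a site to resemble each other. Timing and location of the visits are agreed school by school (section 3.4). An intervention team works through one site for weeks before moving on (section 3.7.4). Referral relies on local providers (section 3.5). In Y-Check 2, circumcision referral, HIV testing and sexual health services are described for the community hubs only (section 3.7.2). The primary outcome requires care or referral to be complete for every condition identified (section 6.1), so hub and school participants can have different numbers of conditions to clear.

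The primary schools in the city are described as all mixed sex (section 3.2), so each Y-Check 1 sex group is spread over the same 4-6 schools. With so few sites, even a modest correlation costs precision.

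Two things are at stake. The first is the honesty of the stated precision. The second is the use made of the results: objective 2(v) in section 2.2 is to supply planning parameters for a larger evaluation. That study would inherit optimistic precision, and it would lack an ICC, which is not on the list of parameters.

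**Working it through.** **Inputs.** From section 6.2: n = 150, p = 0.75 for the primary outcome; n = 50 for a single condition. From section 2.3: 4-6 sites (Y-Check 1), 4-12 sites (Y-Check 2). Assumed, because the protocol gives no value: ICC 0.01-0.05, and sites of equal size.

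**Step 1: the plan's own figures under independence.**
- Primary outcome: 1.96 × √(0.75 × 0.25 / 150) = 1.96 × 0.0354 = 0.069, so ±6.9 points (68.1%-81.9%). The exact interval for 112/150 is 66.9%-81.4%. The stated ±1.7% does not reproduce. It would need 0.75 × 0.25 × (1.96/0.017)² ≈ 2,490 screen-positives, more than the 2000 adolescents in the study.
- Single condition: the exact binomial interval for 38/50 is 61.8%-86.9% (stated 62%-87%). For 25/50 it is 35.5%-64.5% (stated 35%-65%, a match if rounded outward). So the figures that do reproduce are simple binomial intervals with nothing added for clustering.

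**Step 2: add clustering.** With k equal sites, m = 150/k, design effect = 1 + (m − 1) × ICC, half-width = 6.9 × √(design effect). The last column replaces 1.96 with the t quantile on k − 1 degrees of freedom.

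| Sites (k) | m | Assumed ICC | Design effect | Effective n | Half-width (z) | Half-width (t, k−1 df) |
|---|---|---|---|---|---|---|
| 6 | 25 | 0.01 | 1.24 | 121 | ±7.7 | ±10.1 |
| 6 | 25 | 0.05 | 2.20 | 68 | ±10.3 | ±13.5 |
| 4 | 37.5 | 0.01 | 1.36 | 110 | ±8.1 | ±13.1 |
| 4 | 37.5 | 0.05 | 2.83 | 53 | ±11.6 | ±18.9 |
| 12 | 12.5 | 0.01 | 1.11 | 135 | ±7.3 | ±8.2 |
| 12 | 12.5 | 0.05 | 1.58 | 95 | ±8.7 | ±9.8 |

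The rows for 4 and 6 sites cover Y-Check 1. The 4-site rows also describe Y-Check 2 at its minimum (two schools and two hubs), and the 12-site rows describe it at its maximum.

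**Step 3: the single-condition example.** With n = 50 at 75%, the independent normal-approximation half-width is ±12.0. Over 4-6 sites and ICC 0.01-0.05 it becomes about ±12.4 (6 sites, 0.01) to ±15.1 (4 sites, 0.05). The loss is smaller because there are fewer screen-positives per site.

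**The case against.** The strongest reply is that the quoted sentence in section 6.3 is not an error. An individual unit of analysis is compatible with cluster-robust variance or a random site effect, and the choice of variance estimator is commonly left to the statistical analysis plan, which is not available here. This stands. A reader might infer that every interval and the regression will treat participants as independent, but the protocol nowhere says so. The point therefore rests first on section 6.2, which is protocol content and does state precision without a clustering allowance, and on section 6.3 only as an unqualified statement of the unit.

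Other replies also carry weight:
- The size depends on an ICC that the protocol does not give, and it is minor for Y-Check 2 with many sites.
- The two intervention teams move between sites and many referral destinations depend on the condition, which may keep the correlation low.
- Sites are chosen with stakeholders. If the results are meant to describe only these sites, between-site variation matters less. Against this, section 3.2 aims for communities representative of Chitungwiza and objective 2(v) looks to a larger study.
- The before-after comparisons follow the same cohort, so stable differences between sites largely cancel. No widening is claimed for them here.

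A reader might also infer that the health-service determinants in the regression vary only between sites, so that the regression is hit hardest. The protocol does not define these determinants, and some, such as on-the-spot care versus referral, could vary between individuals.

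**Conclusion.** The point holds in this limited form: the stated precision ignores clustering in a visibly clustered design, and section 6.3 does not qualify the individual unit. For a Y-Check 1 sex group, ±6.9 points becomes about ±7.7 to ±11.6, or about ±10 to ±19 with a t quantile suited to few sites. This rests on an assumed ICC of 0.01-0.05, equal school sizes, and the protocol's own 150 screen-positives and 75%. For Y-Check 2 the loss ranges from small (±7.3 with 12 sites and ICC 0.01) to the same as for four schools.

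The baseline of ±6.9 is recomputed and is not the protocol's figure. The gap between ±1.7% and ±6.9 has nothing to do with clustering and should not be counted as part of this effect. Nor do the documents support a definite figure for lost coverage, since that too would depend wholly on the assumed ICC. The primary outcome is descriptive, with no success threshold in section 6.3, so the consequence is overstated precision and not a wrong decision on a test.

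**What to change.** - **Section 6.2:** restate the primary and single-condition precision over an ICC range such as 0.01-0.05, labelled as an assumption, for the smallest and largest planned number of sites. Correct the ±1.7% in the same revision.
- **Section 6.3:** keep the individual as the unit. State that confidence intervals, before-after comparisons and the regression will use a variance that allows for school or hub, either cluster-robust with a small-sample correction or through a site random effect. The detail can go in the statistical analysis plan.
- **Reporting:** give the ICC of the primary outcome with its uncertainty, for use in planning the next-phase study.

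The cost is wider intervals and slightly more analysis. An ICC estimated from so few sites will be imprecise and should be presented as such. Recruitment and care delivery do not change.
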